6.4 Accountability Procedures for the Study Intervention/Investigational Product(s)

All investigational products will be maintained by the pharmacy department and stored separately from the general stock. Upon receipt of the product, an inventory will be performed and contents of the shipment verified. Accountability logs will be maintained by the pharmacy and indicate all investigational product that has been received, dispensed, and destroyed at the site.

6.5 Concomitant Medications/Treatments

All current medications and therapies will be continued during this study with the exception of those listed in the exclusion criteria.

7 STUDY SCHEDULE

7.1 Study Evaluations

Written informed consent will be obtained from the eligible patient's parent or guardian prior to their operative procedure. Consent will be obtained from one of the investigators listed on the study protocol.

Eligible subjects will be randomized to receive standard pain management regimens plus placebo (0.9% saline of equivalent volume) or ketorolac 0.5mg IV q8h x 72h plus standard pain management regimens, post-operatively. The study drug will be started within 24hrs of the operative procedure.

All subjects will undergo daily physical examinations by their operating surgeon and team (including nurse practitioners, surgical residents, surgical fellows, nursing staff). Days on the ventilator, reintubation events, blood urea nitrogen levels, creatinine levels, neonatal pain scores (NPASS), urine output per shift, platelet values, hemoglobin values, blood pressure, amount of opioid used, other medications patient is receiving, intraoperative issue/complications will be recorded.

Patients will have daily laboratory tests including complete blood counts and chemistry panels as would be routine for their postoperative care.

The following laboratory evaluations will be performed daily on patients enrolled in this study, as part of their routine postoperative care. Additional laboratory studies may be obtained as indicated by the patient's condition. Laboratory specimens will be obtained via heelstick, arterial line (if existent), or central venous catheter (if existent). Specimen volumes will be minimalized to 0.5ml per tube.

Hematology: hemoglobin, hematocrit, white blood cells (WBC) with differential count, platelet count.

Biochemistry: blood urea nitrogen, creatinine, electrolytes.

Coagulation profile: protime, prothrombin time, INR

No additional testing will be required by the study, unless signs of renal injury or bleeding events occur.

7.2 Follow-up

The drug/placebo will be administered every 8 hours for 72 hours, unless the medication is stopped earlier due to an AE. Patients will be followed for 48 hours from the completion of the drug/placebo administration. After 48 hours, the study will be concluded for that patient. There will be no further follow-up evaluations or visits.

8 STUDY PROCEDURES/EVALUATIONS

8.1 Specification of Safety Parameters

Events will be collected during the duration of the study, which is 48 hours from the completion of the study drug/placebo.

Bleeding episodes will be defined by following:

- Persistent bloody drainage from a nasogastric tube, resulting in a drop of hemoglobin of greater than or equal to 2g/dL (change of 1g/dL in hemoglobin may be explained by the infusion of perioperative crystalloid, and in the absence of hemodynamic instability would be considered within the acceptable standard deviation)
- Surgical site bleeding resulting in a drop of hemoglobin $>2\text{g/dL}$ from initial postop value, unless the patient has required crystalloid or fluid boluses other than PRBC totalling 60ml/kg or greater.
- Any hemodynamic instability associated with a drop of hemoglobin $>2\text{g/dL}$

2. Renal injury will be defined by the following:

- Patients who are resuscitated but with continued postoperative $\text{UOP} < 0.5\text{ml/kg/h}$ persistent over 8 hours
- A decrease in estimated creatinine clearance by 25%, in a well-resuscitated patient

8.2 Methods and Timing for Assessing, Recording, and Analyzing Safety Parameters

8.2.1 Adverse Events

Adverse Event: ICH E6 defines an AE as any untoward medical occurrence in a patient or clinical investigation subject administered a pharmaceutical product regardless of its causal relationship to the study treatment. An AE can therefore be any unfavorable and unintended sign (including an abnormal laboratory finding), symptom, or disease temporally associated with the use of medicinal (investigational) product. The occurrence of an AE may come to the attention of study personnel during study visits and interviews of a study recipient presenting for medical care, or upon review by a study monitor.

All AEs including local and systemic reactions not meeting the criteria for "serious adverse events" should be captured on the appropriate CRF. Information to be collected includes event description, time of onset, clinician's assessment of severity, relationship to study product (assessed only by those with the training and authority to make a diagnosis, which would include MD, PA, Nurse Practitioner, DO, or DDS), and time of resolution/stabilization of the event. All AEs occurring while on study must

be documented appropriately regardless of relationship. All AEs will be followed to adequate resolution.

Any medical condition that is present at the time that the patient is screened should be considered as baseline and not reported as an AE. However, if it deteriorates at any time during the study, it should be recorded as an AE.

All AEs must be graded for severity and relationship to study product.

Severity of Event: All AEs will be assessed by the clinician using a protocol defined grading system. For events not included in the protocol defined grading system, than the following guidelines will be used to quantify intensity.

Mild: events require minimal or no treatment and do not interfere with the patient's daily activities.

Moderate: events result in a low level of inconvenience or concern with the therapeutic measures.

Moderate events may cause some interference with functioning.

Severe: events interrupt a patient's usual daily activity and may require systemic drug therapy or other treatment. Severe events are usually incapacitating.

Life threatening: any adverse drug experience that places the patient or subject, in the view of the investigator, at immediate risk of death from the reaction as it occurred, ie, it does not include a reaction that had it occurred in a more severe form, might have caused death.

Changes in the severity of an AE should be documented to allow an assessment of the duration of the event at each level of intensity to be performed. Adverse events characterized as intermittent require documentation of onset and duration of each episode.

Relationship to Study Products: The clinician's assessment of an AE's relationship to test article (vaccine or study drug) is part of the documentation process, but it is not a factor in determining what is or is not reported in the study. If there is any doubt as to whether a clinical observation is an AE, the event should be reported. All AEs must have their relationship to study product assessed using the terms: associated or not associated. In a clinical trial, the study product must always be suspect. To help assess, the following guidelines are used.

- Associated – The event is temporally related to the administration of the study product and no other etiology explains the event.
- Not Associated – The event is temporally independent of study product and/or the event appears to be explained by another etiology.

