3.2 Study Outcome Measures

3.2.1 Primary Outcome Measures

Primary: The primary purpose of this study is to compare bleeding events in neonates who receive ketorolac and those who do not receive ketorolac. We hypothesize that ketorolac is safe and effective in infants \geq 37wks corrected gestational age and at least one week of age. Primary outcomes measured include bleeding events and renal injury.

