8.3 Reporting Procedures

8.3.1 Regulatory Reporting for Studies Conducted Under a Sponsor-Investigator IND

Following notification to the investigator, the Sponsor Investigator, will report events that are both serious and unexpected and that are associated with study product(s) to the Food and Drug Administration (FDA) within the required timelines as specified in 21 CFR Part 312.32: fatal and life-threatening events within 7 calendar days (by phone or fax) and all other SAEs in writing within 15 calendar days. All serious events designed as "not associated" to study product(s), will be reported to the FDA at least annually in a summary format.

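### The two-label causality rule has no place for contribution, so a serious unexpected postoperative event with a competing surgical cause can go to the annual summary instead of expedited reporting.

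*Protocol*

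**What the plan says.** Section 8.2.1 of the protocol sets a two-way classification: "All AEs must have their relationship to study product assessed using the terms: associated or not associated". The guideline for the first label is "The event is temporally related to the administration of the study product and no other etiology explains the event". The guideline for the second is "The event is temporally independent of study product and/or the event appears to be explained by another etiology". Just before these, the section says "In a clinical trial, the study product must always be suspect", and it says of the clinician's assessment that "it is not a factor in determining what is or is not reported in the study".

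Section 8.3.1 then uses the label. The sponsor-investigator "will report events that are both serious and unexpected and that are associated with study product(s) to the Food and Drug Administration (FDA"), within 7 calendar days if the event is fatal or life-threatening and within 15 otherwise. Serious events labelled not associated "will be reported to the FDA at least annually in a summary format".

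Section 3.2.1 says "Primary outcomes measured include bleeding events and renal injury". Under sections 5.1 and 6.2, all randomised infants have surgery on the abdomen or chest and receive the first dose within 24 hours of its end.

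**The concern.** The two labels do not carry the same burden. To implicate the product, no other cause may explain the event. To clear it, another cause need only appear to do so. An event with two causes, such as a surgical-site bleed prolonged by a drug that impairs platelet function (the mechanism given in section 2.1), has an apparent surgical cause and is cleared under the written rule.

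In this population a competing cause is part of the design, because all infants are dosed shortly after major surgery, and the events of interest are ones that surgery can also produce. Since the label is one of the conditions for expedited reporting, the rule can delay news to the regulator of a serious event to which ketorolac contributed. The stated purpose of the trial is to characterise safety. Section 9 says site monitoring does not apply, and section 5.3.4 gives no trigger for the safety evaluation it mentions, so the timing of regulatory reports matters more than it otherwise would.

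**Working it through.** The protocol states no figure that bears on this point, so there is none to reproduce. The check is mainly one of logic.

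**1. The labels (section 8.2.1).**
- Associated = temporally related AND no other cause explains the event.
- Not associated = temporally independent OR another cause appears to explain the event. The and/or makes either condition enough.

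**2. The reporting gate (section 8.3.1).**
- Expedited = serious AND unexpected AND associated.
- Summary at least annually = serious AND not associated.
- Serious, associated but expected: section 8.3.1 states no route.

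**3. Applying both to a serious, temporally related event.**

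| Event | Label as written | Route as written | If contribution counted as associated |
|---|---|---|---|
| Unexpected, no other cause | Associated | 7 or 15 days | Unchanged |
| Unexpected, surgical cause apparent, product contribution plausible | Not associated | Annual summary | 7 or 15 days |
| Expected, surgical cause apparent, product contribution plausible | Not associated | Annual summary | Associated but not expedited; no route stated |
| Surgical cause apparent, product contribution not plausible | Not associated | Annual summary | Unchanged |

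The second row is the defect. The third row shows that a change to the causality wording alone is incomplete.

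**4. Which events fall in the second row.** Section 2.3.1 lists bleeding and renal insufficiency as known risks of ketorolac, each at 1-3%. The protocol does not say which document, or what severity, decides whether an event is unexpected. A fatal bleed, for example, is not listed there. If it counts as unexpected, the causality label decides its route.

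**5. Length of the delay in terms of enrolment.** Inputs are 50 infants (sections 5 and 5.3.1) and 1-2 years to complete (section 5). Assuming even enrolment:
- 50 infants / 2 years = 25 infants per year
- 50 infants / 1 year = 50 infants per year

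So 25 to 50 infants, half to all of the trial, could be enrolled within one full annual interval. This is an upper limit on the delay: an event shortly before a summary is due would wait less. The Protocol Summary gives 60 infants instead of 50; the same arithmetic then gives 30 to 60, again half to all.

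**The case against.** The strongest reply is that the safety signal is not lost. Bleeding and renal injury are primary outcomes, and their definitions in section 8.1 do not use the causality label. All adverse events are documented regardless of relationship (8.2.1), and all serious ones are recorded, followed and reviewed by a study clinician (8.2.2). Bleeding and renal data are reviewed at least daily by study physicians and a pharmacist (5.3.3). A bleeding event or worsening renal function leads to unblinding and an end to study product with no causality test (5.3.4). All of this stands, and it confines the defect to the labels and the timing of regulatory reports.

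A second reply is that the definitions are offered as guidelines to qualified clinicians, directly after the reminder to suspect the product, and that they ask whether another cause explains the event, not whether one is merely available. This stands in part. A reader might infer that almost every postoperative bleed or renal event is cleared by construction. The documents do not support that. Surgery does not automatically explain persistent bloody nasogastric drainage, or a fall in creatinine clearance in a well-resuscitated infant. The exclusions in section 5.2 also remove several competing causes, among them known renal disease, rising creatinine, nephrotoxic or haemostasis-affecting drugs, disseminated intravascular coagulation and recent gastrointestinal bleeding. But the second label is met once another cause appears to explain the event, so the lean in one direction remains.

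A third reply is that many such events would miss expedited reporting anyway because they are expected. That is correct, and it means the causality wording is not the only gate. It does not protect the events that are unexpected.

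Finally, the statement that relationship does not decide what is reported concerns reporting within the study, whereas section 8.3.1 concerns the regulator. The two can be read together, so this is a point to clarify and not a flat contradiction.

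**Conclusion.** The point holds in a limited form. As written, the rule can label as not associated a postoperative event to which ketorolac contributed. The case is strongest for surgical-site bleeding and weaker for renal injury. For a serious and unexpected event, that label moves the report from 7 or 15 days to a summary due at least yearly, during which up to 25-50 of the 50 infants could be enrolled. This rests on even enrolment over the stated 1-2 years and on clinicians applying the guidelines as worded. The randomised comparison is not affected.

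The number of reports affected cannot be estimated from the protocol. A reader might take the 4 of 53 bleeds (7.5%) in the retrospective cardiac-surgery series of section 2.1 and expect 25 x 4/53 = 1.9 misclassified events in the ketorolac arm. That does not follow: those bleeds were minor, without significant haemoglobin change or transfusion, and as described would not meet the haemoglobin-drop definitions in section 8.1. The 1-3% in section 2.3.1 would give 25 x 0.01 = 0.25 to 25 x 0.03 = 0.75 bleeds, without regard to seriousness or expectedness.

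Nor should the trial be read as the first use of ketorolac at this age. Section 2.1 describes earlier neonatal use, section 2.2 claims only the first known study exclusively in this group, and the appended guideline already lists the drug. Whether the rule satisfies the regulation cited in section 8.3.1 cannot be judged from the protocol.

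**What to change.** 1. In section 8.2.1, redefine the labels. *Associated: there is a reasonable possibility that the study product caused or contributed to the event. Not associated: the event is temporally independent of the study product, or another cause explains it and a contribution of the product is not plausible.*
2. Reconcile 8.2.1 with 8.3.1: say that relationship plays no part in what is recorded in the study but is one condition for expedited reporting.
3. In section 8.3.1, name the reference against which an event is judged unexpected, including how severity counts, since section 2.3.1 already lists bleeding and renal insufficiency. Without this, the first change may not bring such events into expedited reporting.
4. In the same section, state the route for serious events that are associated but expected, so that relabelled events do not drop out of the annual summary.

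The cost is a text amendment and possibly a few more expedited reports. Data collection, the outcome definitions and the comparison by arm stay as they are.

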8.2.2 Serious Adverse Events

Serious Adverse Event (SAE): An SAE is defined as an AE that meets one of the following conditions:

Death during the period of protocol defined surveillance

Life-threatening event (defined as a subject at immediate risk of death at the time of the event)

An event requiring inpatient hospitalization or prolongation of existing hospitalization during the period of protocol defined surveillance

Results in a persistent or significant disability/incapacity

Any other important medical event that may not result in death, be life threatening, or require hospitalization, may be considered a serious adverse experience when, based upon appropriate medical judgment, the event may jeopardize the subject and may require medical or surgical intervention to prevent one of the outcomes listed above. Examples of such medical events include allergic bronchospasm requiring intensive treatment in an emergency room or at home, blood dyscrasias or convulsions that do not result in inpatient hospitalization, or the development of drug dependency or drug abuse.

All SAEs will be:

- recorded on the appropriate SAE source document
- followed through resolution by a study clinician
- reviewed and evaluated by a study clinician

8.2.3 Procedures to be followed in the Event of Abnormal Laboratory Test Values or Abnormal Clinical Findings

Bleeding will be closely monitored in the NICU setting. Daily CBC's are obtained during the postoperative period, and these will be recorded as data relevant to the study. Deviations in hemoglobin or platelet counts will be detected, and treated as is standard of care. If concern arises about the drug, the patient will be unblinded and pulled from receiving the study drug or placebo. However, events will still be recorded on the patient. Collection of laboratory data should be limited to those laboratory parameters that are relevant to safety, study outcome measures, and/or clinical outcome.

8.3 Reporting Procedures

8.3.1 Regulatory Reporting for Studies Conducted Under a Sponsor-Investigator IND

Following notification to the investigator, the Sponsor Investigator, will report events that are both serious and unexpected and that are associated with study product(s) to the Food and Drug Administration (FDA) within the required timelines as specified in 21 CFR Part 312.32: fatal and life-threatening events within 7 calendar days (by phone or fax) and all other SAEs in writing within 15 calendar days. All serious events designed as "not associated" to study product(s), will be reported to the FDA at least annually in a summary format.

9 CLINICAL MONITORING

Site monitoring is not applicable for this single center pilot study.

10 STATISTICAL CONSIDERATIONS

10.1 Study Hypotheses

We hypothesize that ketorolac is safe and effective in infants \geq 37wks corrected gestational age and at least one week of age.

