SMC	Safety Monitoring Committee
SOP	Standard Operating Procedure
US	United States
WHO	World Health Organization

PROTOCOL SUMMARY

Title:	The Safety of Ketorolac in Surgical Neonates
Phase:	II
Population:	Neonates aged 1 week to 3 months who undergo an abdominal, cardiac, or thoracic surgical procedure at Nationwide Children's Hospital, Columbus, Ohio. Sample size will include 60 patients.
Number of Sites:	Nationwide Children's Hospital, Columbus, Ohio
Study Duration:	1-2 years
Subject Participation Duration:	Five days
Description of Agent or Intervention:	Ketorolac 0.5mg/kg (or placebo, 0.9% normal saline) intravenous every 8 hrs for 72hrs. First dose administered within 24hrs following the completion of the surgical procedure.
Objectives:	
Primary: The primary purpose of this study is to compare bleeding events in neonates who receive ketorolac and those who do not receive ketorolac. We hypothesize that ketorolac is safe and effective in infants \geq 37wks corrected gestational age and at least one week of age.
 
Secondary: We intend to evaluate daily creatinine levels, pain scores, urine output per shift, platelet counts, hemoglobin levels, number of days on the ventilator, amount of opioid administered, blood pressure, and reintubation events on all patients in this study as secondary study points.

Description of Study Design:	See schematic below
Estimated Time to Complete Enrollment:	1-2 years

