2.3 Potential Risks and Benefits

2.3.1 Potential Risks

Risks of ketorolac include the potential for bleeding events (1-3% in population), the risk of renal insufficiency (1-3% in population), and the risk of hypersensitivity reactions. These are accepted risks when using ketorolac in older infants, children, and adults. While these risks are small, the seriousness of such risks may be much greater and may involve the need for blood transfusions, additional procedures and/or reoperations, or additional laboratory or radiological studies.

Bleeding episodes will be defined by following:

1. Persistent bloody drainage from a nasogastric tube, resulting in a drop of hemoglobin of greater than or equal to 2g/dL (change of 1g/dL in hemoglobin may be explained by the infusion of perioperative crystalloid, and in the absence of hemodynamic instability would be considered within the acceptable standard deviation)
2. Surgical site bleeding resulting in a drop of hgb >2 g/dL from initial postop value, unless the patient has required crystalloid or fluid boluses other than PRBC totalling 60ml/kg or greater.
3. Any hemodynamic instability associated with a drop of hemoglobin >2 g/dL

Several published criteria for adults and children exist to enable the practitioner to identify early signs of renal injury (9-11). Of these, the Pediatric modification of the Risk, Injury, Failure, Loss, End-Stage Renal Disease (p-RIFLE) criteria are probably the most reliable in this population, as this has been validated in children.

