5.3 Treatment Assignment Procedures

5.3.1 Randomization Procedures

This trial is randomized. Patients will be randomized according to a fixed 1:1 allocation. The overall sample size will be 50 patients, 25 in each group. The randomization scheme will consist of a permuted block randomization in which the blocking factor varies randomly between 4 and 6.

Randomization will be stratified by pain category (moderate and severe, refer to pain management guidelines).

An observational arm was added for those patients who do not wish to be randomized. If consent is obtained for this arm of the study, then study staff will be allowed to follow and record clinical data as applicable and stated for this study. Patients will receive postoperative pain control as per the discretion of their primary provider.

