10.2 Sample Size Considerations

This is a pilot study for safety. There are no statistical considerations for these small numbers. This study will hopefully provide some background data for a large scale, multi-center study with statistical significance.

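### The hypothesis that ketorolac is safe and effective does not fit the design: about 25 infants per arm cannot support a safety conclusion from a null bleeding comparison, and no criterion for efficacy is set

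*Protocol*

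**What the plan says.** All statements are in the Protocol.

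- **Hypothesis.** Section 10.1 consists of one sentence, which begins "We hypothesize that ketorolac is safe and effective in infants". The same sentence stands in the Protocol Summary, 2.2 and 3.2.1. No null or alternative hypothesis, margin or threshold accompanies it.
- **Primary outcomes.** Section 3.2.1 gives the primary purpose as a comparison of bleeding between infants with and without ketorolac, and adds: "Primary outcomes measured include bleeding events and renal injury". Opioid amount, pain scores and ventilator days are secondary (3.2.2).
- **Sample size.** Section 5.3.1: "The overall sample size will be 50 patients, 25 in each group"; section 5 agrees. The Protocol Summary says "Sample size will include 60 patients".
- **Statistical basis.** Section 10.2 calls the trial a pilot for safety, says "There are no statistical considerations for these small numbers", and hopes for background data for a larger multi-centre study.
- **Event rates.** Section 2.3.1: "Risks of ketorolac include the potential for bleeding events (1-3% in population), the risk of renal insufficiency (1-3% in population". These are general risks of the drug, not rates assumed for either arm. Section 2.1 cites a retrospective review in which 4 of 53 infants under 6 months (7.5%) had minor bleeding on ketorolac.

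**The concern.** A hypothesis placed under Statistical Considerations is what the trial report will be measured against. Here it is worded as a conclusion about safety and efficacy. The only stated route to the safety half is a between-arm comparison of uncommon binary events in a very small sample, with no margin. The next subsection then disclaims any statistical basis. The efficacy half has no primary outcome.

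What is at stake is how a clean result may be reported. If few or no bleeds occur, the arms will not differ significantly, and the sentence in 10.1 invites the comment that the hypothesis was supported. The data would still be compatible with a bleeding risk several times the one quoted in 2.3.1. The protocol's own background (2.1) describes a 75-patient randomized trial in which the absence of significant differences led to a conclusion of safety, so this way of reasoning is close at hand.

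**Working it through.** **The plan's own figure.** There is none to reproduce: no alpha, power, effect size or margin is given. A two-sided 0.05 level and, where needed, 80% power are assumed below.

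**Inputs.** n = 25 per arm (5, 5.3.1), with 30 per arm as a check. The 30 assumes that all 60 patients in the Summary are randomized 1:1. Bleeding rates are 1–3% (2.3.1) and 7.5% (2.1). Using either as the placebo rate is an assumption. The 7.5% comes from treated infants with minor episodes that did not change haemoglobin significantly, whereas the trial's definition requires a fall of about 2 g/dL.

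**1. Expected events.** 25 × 0.01 = 0.25 to 25 × 0.03 = 0.75 per arm, so 0.5 to 1.5 in the whole trial.

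**2. Chance of no bleed among 25 ketorolac infants**, (1 − p)^25:

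| True rate p | Chance of zero events |
|---|---|
| 1% | 78% |
| 3% | 47% |
| 7.5% | 14% |
| 10% | 7% |

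**3. What a clean arm rules out.** The exact (Clopper–Pearson) two-sided 95% upper limit for zero events is 1 − 0.025^(1/n).

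- 0/25: 1 − 0.025^(1/25) = 13.7%, which is 13.7/3 = 4.6 times the top of the quoted range.
- 0/30: 1 − 0.025^(1/30) = 11.6%.
- 1/25: 20.4%. 2/25: 26.0%.

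For the difference between arms with 0/25 in each, the Newcombe limits are ± z²/(n + z²) = ± 3.84/28.84 = ± 13.3 points.

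**4. Power of a two-sided Fisher test**, by full enumeration of the two binomial distributions:

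| Placebo vs ketorolac | 25 per arm | 30 per arm |
|---|---|---|
| 3% vs 6% | 0.2% | 0.3% |
| 3% vs 9% | 1.2% | 2.1% |
| 7.5% vs 22.5% | 19% | 23% |
| 3% vs 35% | 81% | 87% |

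At 25 per arm, five bleeds against none gives p = 0.0502, so six against none are needed for significance. For scale, 80% power for 3% versus 9% needs about 245 per arm (normal approximation; 278 with continuity correction).

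**5. Renal injury.** No rate is given for the definition in 8.1 (low urine output over 8 hours, or a 25% fall in estimated creatinine clearance), so steps 1, 2 and 4 cannot be carried over to it. The limits in step 3 depend only on the counts and apply to either outcome. If the event were common, the interval would be wider. As an illustration, 20% in each arm gives 1.96 × √(2 × 0.2 × 0.8/25) = ± 22 points.

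**6. Efficacy.** The harm rates do not enter here. For a continuous outcome at 25 per arm, the difference detectable with 80% power is (1.96 + 0.84) × √(2/25) = 0.79 SD (0.81 SD with the t distribution). Power for 0.5 SD is 42%. The protocol gives no SD or target difference against which to judge this.

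**The case against.** Several points on the other side are sound.

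- **The protocol limits its own claim.** Section 10.2 calls this a pilot and leaves statistical significance to a later study; 3.1 states the purpose as characterizing the safety profile. A reader might infer from 10.1 that a null comparison will be declared proof of safety. No section says so, and no decision rule is written. This point stands. What remains is that 10.1 and 10.2 do not fit each other, and nothing in the text prevents that reading.
- **The event rates say nothing about efficacy.** A reader might infer that the design can support neither half of the hypothesis. The documents do not bear that out: a large effect on opioid use is within reach (step 6). The fair objection is that no efficacy outcome is primary and no criterion is set.
- **A null is not guaranteed whatever the drug does.** A very large harm, such as 3% versus 35%, would be found about 80% of the time. The claim must be confined to harms such as a doubling or tripling.
- **The 1–3% range is a general figure.** This is correct, and the true rate under the trial's definitions is unknown. At 7.5% the chance of missing a tripling is still about 81%.
- **Analysis detail belongs in the SAP.** Also correct: the interval method, baseline adjustment and laboratory summaries may properly be left there, and their absence is no fault. The hypothesis, primary outcomes and sample-size statement are fixed in the protocol.
- **The later trial.** Section 10.2 promises only background data. It does not say that a later trial would be sized on this trial's point estimate.

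**Conclusion.** The concern holds in this limited form. At 25 per arm, a non-significant bleeding comparison is about 99% likely if the true rates are 3% and 9%, and about 81% likely if they are 7.5% and 22.5%. It therefore cannot support a statement that ketorolac is safe. Zero events in 25 leaves rates up to 13.7% open. At 30 per arm the limit is 11.6% and the conclusion is unchanged.

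The power figures rest on assumed placebo rates, a 0.05 two-sided level and Fisher's test; the confidence limits rest only on the counts. For renal injury, only the confidence limits can be stated. The efficacy part is a mismatch between the hypothesis and the outcomes, not a shortage of patients.

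Severity is should-fix. The correction changes what the trial may conclude, but not its allocation, data collection or safety monitoring, and 10.2 already disclaims part of the inference.

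**What to change.** 1. Reconcile the sample size: 50 in sections 5 and 5.3.1, 60 in the Summary.
2. Restate 10.1 as an estimation objective: to estimate the ketorolac-minus-placebo difference in the proportion of infants with at least one bleeding episode, and in the proportion with renal injury, each with a 95% confidence interval. The interval method can stay with the SAP.
3. Add that absence of a significant difference will not be taken as evidence of safety.
4. Remove the efficacy claim from the hypothesis, or label opioid use and pain scores as exploratory.
5. In 10.2, replace the sentence "There are no statistical considerations for these small numbers" with the precision at the reconciled size. For 25 per arm: 0, 1 or 2 events give exact 95% upper limits of 13.7%, 20.4% and 26.0%, and no events in either arm gives a difference interval of ± 13.3 points. For 30 per arm, 0 events gives 11.6%.
6. Make the same wording changes in the Summary, 2.2 and 3.2.1.

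The cost is wording only: no extra patients or measurements. The downside is that the stated claim becomes less favourable.
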